4.2 Exclusion Criteria

1. Patients in whom media opacities (cornea, anterior or posterior synechia, cataract, vitreous haze and others) of either eye preclude investigation and documentation of the posterior pole and intravenous fluorescein angiography, or optical coherence tomography evaluation in the study eye.
2. Patients receiving any local.
3. Treatment with cyclophosphamide or chlorambucil.
4. Intravitreal injections (including but not limited to anti-vascular endothelial growth factors) 60 days prior to the baseline.
5. Posterior subtenon's injection or orbital floor injection of steroids 90 days prior to Baseline.
6. Any implantable corticosteroid-eluting device (Ozurdex, Iluvien, Retisert, triamcinolone intravitreal implant, fluocinolone intravitreal implant) in the study eye, with the following exceptions:

- If the device had been removed more than 90 days prior to Day 0 of this study, the eye will be eligible for PP-001-1001.
- If Ozurdex had been implanted 6 months before Day 0 of this study, the eye will be eligible for PP-001-1001.
- If Iluvien or Retisert had been implanted 3 years before Day 0 of this study, the eye will be eligible for PP-001-1001.

7. Intraocular surgery within 90 days prior to Day 0 in the study eye.
8. Capsulotomy within 30 days prior to Day 0 in the study eye.
9. History of vitreoretinal surgery or scleral buckling within 90 days prior to Day 0 in the study eye.
10. Any ocular surgery (including cataract extraction or capsulotomy) of the study eye anticipated within the first 60 days following Day 0.
11. Intraocular pressure ≥ 25 mmHg in the study eye (glaucoma patients maintained on no more than one topical medication with IOP < 25 mmHg are allowed to participate).
12. Ocular hypotonia (IOP less than 6 mmHg).
13. Pupillary dilation inadequate for quality fundus photography in the study eye.
14. Aphakia or anterior chamber lens in the study eye.
15. Visible scleral thinning, scleral ectasia or keratoconus in the study eye.
16. Presence of any ocular malignancy.
17. Ocular or periocular infection in either eye or the use of systemic antibiotics.
18. Participation in other investigational drug or device clinical trials within 90 days prior to Day 0, or planning to participate in other investigational drug or device clinical trials within 180 days following Day 0. This includes both ocular and non-ocular clinical trials.
19. Female patients who are of childbearing potential or who are pregnant.
20. Use of any anticoagulant or thrombocyte aggregation inhibiting agent (marcumar, warfarin, heparin, enoxaparin, apixaban, rivaroxaban, pentosanpolysulfate, dabigatran, aspirin and others) less than 14 days prior to injection visit (Day 0).
21. Known allergy or hypersensitivity to the study medication, any component of the delivery vehicle, any corticosteroids or any diagnostic agents used during the study (e.g., fluorescein, dilation drops, antibiotic drops and povidone).
22. Patients with diagnosis of any acute or chronic systemic illness other than uveitis.

5. STUDY DRUG ADMINISTRATION

See Section 8 for a complete description of study drugs. Instructions for the preparation of the study drugs will be provided in a Pharmacy Manual.

5.1 Randomization

This is a non-randomized study. Patients will be assigned to the next available cohort as they are recruited to the study.

5.2 Study Drug Treatment

5.2.1 Duration of Treatment

Patients will receive a single intraocular dose of PP-001.

5.2.2 Post-Baseline Treatment Modifications

The results from each dosing day will be reviewed before progressing with the subsequent dosing day. Dosing in the next cohort will only commence with dosing after the previous cohort has completed all study sessions up to day 28 and no safety issues have been identified after being reviewed by the SDBM.

5.3 Timing of Dosing and Dose Administration

The study drug will be administered on Day 0 following the completion of all pre-dose procedures.

5.4 Preparation of Treatment

A Pharmacy Manual will be provided to investigative sites with additional details on preparation of study drug material.

5.5 Blinding

This is an open-label study.

5.6 Unblinding of Therapy Assignments

As this is an open-label study, unblinding will not be required.

5.7 Adherence

Throughout the study, hospital staff or study personnel will administer all doses of study drug. The date, start and stop time of each dose will be recorded in the electronic case report form (eCRF).

5.8 Occupational Safety

PP-001 is not expected to pose any occupational safety risk to site staff under normal conditions of use and administration.

A Material Safety Data Sheet describing occupational hazards and recommended handling precautions either will be provided to the Investigator, where this is required by local laws, or is available upon request from Panoptes Pharma GesmbH.

In line with good handling of chemical products, precautions are to be taken to avoid skin and eye contact. In the case of unintentional occupational exposure, any signs or symptoms should be treated appropriately and the Sponsor notified.

6. STUDY ASSESSMENTS AND PROCEDURE

A schedule of study procedures is presented in Table 1. Patients meeting the eligibility criteria listed in Section 4 may be enrolled in the study after the nature and purpose of the protocol have

been explained and written informed consent to participate has been voluntarily given. Study personnel must complete all screening procedures after informed consent is signed and before the first dose of study drug. Note: assessments performed as part of routine standard of care before consent may be used to satisfy study screening requirements; however, no study-specific procedures may be performed before informed consent is given.

The time and day on which PP-001 is administered will be regarded as 0 h on Day 0. The Investigator should make every effort to perform procedures at the scheduled times and to record the actual time of the procedures, where appropriate, in the patient's eCRF.

For patients who are screened (i.e., those with signed written informed consent) but do not meet the screening criteria, the reason for screening failure will be recorded.

6.1 Surgical Procedure

The study treatment procedure must be performed only by the qualified Investigator in an operating room, surgical suite, or in an office setting using sterile technique. The study medication kit should be readily available during the procedure. The final diluted PP-001 solution will be injected at the required dose at a volume of 100 μ L (see Section 8). For safety reasons, an emergency pars plana vitrectomy aiming at removal of injected drug will be available in case of a severe adverse event including, but limited to, acute loss of visual acuity or acute inflammatory or toxic response to injection. It is therefore mandatory for patients to remain in the hospital for at least 4 hours after the injection procedure.

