Study Drug Assignment: Patients will be dosed in ascending order with 0.3, 0.6, 1.2 or 2.1 µg PP-001 depending on the cohort to which they are assigned.

Duration of Treatment: Patients will receive a single dose of PP-001.

Study Drug Administration: PP-001 will be administered as a single intravitreal injection, which will be performed under sterile conditions in an operating room setting. For safety reasons an emergency pars plana vitrectomy aiming at removal of injected drug will be available in case of a severe adverse event including, but not limited to, acute loss of visual acuity or acute inflammatory or toxic response to injection. It is therefore mandatory for patients to remain in the hospital for at least 4 hours after the injection procedure.

Blinding: This is an open-label study.

Study Design: This prospective, multi-centre, open-label, non-randomized, consecutive study will be conducted in accordance with the European Union (EU) Clinical Trial Directive 2001/20/EC and 2005/28/EC, The Medicines for Human Use (Clinical Trials) Regulations 2004 and current amendments, the Declaration of Helsinki (revised version of Edinburgh, Scotland 2000), Good Manufacturing Practice (GMP), Good Clinical Practice (GCP) and the current national regulations and guidelines, approved by both the local ethics committee and regulatory authority. Eighteen patients older than 18 years of age will be enrolled and receive a single intravitreal injection of PP-001. Patients must have chronic, posterior uveitis, intermediate uveitis or panuveitis requiring treatment and have been receiving an adequate therapy of e.g. systemic corticosteroid treatment or immunosuppressive therapy (e.g. azathioprine, methotrexate, cyclosporine, mycophenolate, tacrolimus) or any combination thereof. Any systemic therapy at study start should be continued throughout the study. Patients must have best-corrected Early Treatment Diabetic Retinopathy Study (ETDRS) visual acuity of 10 letters

or better (approximately 1/35 or 0.032) but equal or less than 50 letters (approximately 20/100 or 0.2) in the study eye.

The study will involve eight inpatient visits (Screening, Baseline, the day of injection [Day 0] and Days 2, 7, 14, 21 and 28) and telephone calls on Day 1 and on Day 40.

Patients will be divided into three cohorts of four patients. Patients will receive the following treatments administered as a single intravitreal injection:

- Cohort 1 will receive 0.3 µg of PP-001

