Variables for Analysis:**Primary**

- Safety parameters (i.e., changes in clinical signs and symptoms from ophthalmic exam, and AEs)

Secondary

- Improvement of inflammation or of any other parameter determined at the ophthalmic examination following the injection of PP-001
- The concentration of PP-001 in plasma at Screening, 4 h ± 1 h after dosing and on Day 2

Safety analysis

The incidence of treatment-emergent adverse events (TEAEs), SAEs, deaths and discontinuations of study drug due to an AE or SAE will be summarized by System Organ Class and Preferred Term according to the Medical Dictionary for Regulatory Activities, by relationship to study drug, and by severity. The incidence of potentially clinically significant vital signs will be summarized.

Pharmacokinetic analysis

The concentration of PP-001 in plasma will be measured in blood samples taken at Screening, 4 h ± 1 h after dosing and on Day 2.

Table 1. Schedule of Assessments and Procedures

| Phase | Screening | Baseline ⁱ | Pre injection | Post injection | Telephone call ^a | Safety visits | | | | | Telephone call ^a |
|--|------------------|-----------------------|---------------|------------------|-----------------------------|---------------|-----------|------------|------------|-------------------------|-----------------------------|
| Day | -14 up to dosing | -7 up to dosing | 0 | 0 | 1 | 2 | 7 +/-1 | 14 +/-1 | 21 +/-1 | 28 ^h +/-1 | 40 |
| Electroretinography | | X | | | | | | X | | X | |
| Fluorescein angiogram | X | | | | | | | | | X | |
| Optical coherence tomography | | X | | | | X | X | X | X | X | |
| Best corrected visual acuity (ETDRS) | X | X | | | | X | X | X | X | X | |
| Visual field (computerized, 30°) | | X | | | | | X | | | X | |
| Visually evoked cortical potential | X | | | | | | | | | X | |
| Intraocular pressure | X | X | | X ^b | | X | X | X | X | X | |
| Slit lamp examination ^c | X | X | X | X ^b | | X | X | X | X | X | |
| Dilated fundoscopy ^d | X | X | | X ^b | | X | X | X | X | X | |
| Study drug injection | | | | X | | | | | | | |
| Blood sampling for PK analysis | X | | | X ^{b,e} | | X | | | | | |
| Corneal endothelial microscopy | | X | | | | | X | | | X | |
| Fundus photography | | X | | | | | | | | X | |
| Amsler grid | | X | | | | X | X | X | X | X | |
| Medical and ophthalmic histories | X | X | | | | | | | | | |
| Vital signs ^f | X | X | X | | | X | X | X | X | X | |
| Twelve-lead electrocardiogram | X | | | | | | | | | X | |

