1.3.2 Pharmacokinetics and Product Metabolism

Pharmacokinetic and metabolic parameters have been evaluated in several *in vitro* and *in vivo* experiments in various species.

PP-001 exhibited strong *in vitro* plasma protein binding properties with bound fraction levels of >99.9%. PP-001 exhibited high metabolic stability after incubation with human liver microsomes. Inhibition potential towards human Cytochrome P450 enzymes was detected but considered insignificant due to low systemic PP-001 exposure after intravitreal administration.

Following intravitreal administration of 60 to 250 µg PP-001 per animal, systemic exposure in the low ng/ml range was detected. Systemic exposure at efficacious human doses (0.6–1 µg/eye) is expected to be even lower. The half-life of PP-001 after intravitreal injection in rabbits was between 12 and 21 hours in ocular tissues and between 5 and 6 hours in peripheral blood. PP-001 does not elicit ocular melanin binding properties as shown in an *in vivo* ocular distribution study that compared pigmented rats with albino rats.

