3. STUDY DESIGN

This prospective, multi-centre, open-label, non-randomized, consecutive study will be conducted in accordance with the European Union (EU) Clinical Trial Directive 2001/20/EC and 2005/28/EC, The Medicines for Human Use (Clinical Trials) Regulations 2004 and current amendments, the Declaration of Helsinki (revised version of Edinburgh, Scotland 2000), Good Manufacturing Practice (GMP), Good Clinical Practice (GCP) and the current national regulations and guidelines, approved by both the local ethics committee and regulatory authority.

Eighteen patients older than 18 years of age will be enrolled and receive a single intravitreal injection of PP-001. Patients must have chronic, posterior uveitis, intermediate uveitis or panuveitis requiring treatment and have been receiving an adequate therapy of e.g. systemic corticosteroid treatment or immunosuppressive therapy (e.g. azathioprine, methotrexate, cyclosporine, mycophenolate, tacrolimus) or any combination thereof. Any systemic therapy at study start should *be continued throughout the study*. Patients must have best-corrected Early Treatment Diabetic Retinopathy Study (ETDRS) visual acuity of 10 letters or better

(approximately 1/35 or 0.032) but equal or less than 50 letters (approximately 20/100 or 0.2) in the study eye.

Patients must give written consent for the study before any study assessments are performed. Screening assessments will be performed 8–14 days before dosing. Baseline assessments will be performed no more than 7 days before injection. The study will involve eight study visits (Screening, Baseline, the day of injection (Day 0) and Days 2, 7, 14, 21 and 28) and telephone calls on Day 1 and Day 40.

Patients will be divided into three cohorts of four patients. Patients will receive the following treatments administered as a single intravitreal injection:

- Cohort 1 will receive 0.3 µg of PP-001
- Cohort 2 will receive 0.6 µg of PP-001
- Cohort 3 will receive 1.2 µg of PP-001

The patients within a cohort will be dosed consecutively with a minimum time interval of 7 days between the dosing of the previous patient and the dosing of the next patient. The results from each dosing day will be reviewed before progressing towards the subsequent dosing day. The next cohort will only receive PP-001 after the previous cohort has completed all study sessions up to Day 28 and no safety issues have been identified after reviewed by the Safety data management board (SDMB).

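### Acute acuity loss is a named trigger for removing the drug, but acuity is not measured after injection until Day 2, so an unreported loss can be missed while most of the drug is still in the eye

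*Protocol*

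**What the plan says.** Protocol 6.1 states that "an emergency pars plana vitrectomy aiming at removal of injected drug will be available" and ties it to a short description of events: "in case of a severe adverse event including, but limited to, acute loss of visual acuity or acute inflammatory or toxic response to injection". The synopsis (Study Drug Administration) describes the same rescue with one word more: "including, but not limited to, acute loss of visual acuity or acute inflammatory or toxic response to injection". Both then draw the same consequence: "It is therefore mandatory for patients to remain in the hospital for at least 4 hours after the injection procedure".

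In Table 1 of the protocol the acuity row reads "Best corrected visual acuity (ETDRS) | X | X | | | | X | X | X | X | X". The columns run Screening, Baseline, Day 0 pre-injection, Day 0 post-injection, Day 1 call, Day 2 and onwards. The three blank cells are therefore both Day 0 columns and the Day 1 call. The table in SAP 3.2 has the same pattern.

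After injection on Day 0, Table 1 marks intraocular pressure, slit lamp, dilated fundoscopy, a pharmacokinetic sample, and adverse and serious events. Protocol 6.8 makes Day 1 a telephone interview that asks about blurred vision and a change in acuity, among other things.

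On kinetics, Protocol 1.3.2 says: "The half-life of PP-001 after intravitreal injection in rabbits was between 12 and 21 hours in ocular tissues". Protocol 3.2 expects an ocular half-life under 20 h in patients.

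**The concern.** The plan names a sign, keeps the patient in hospital because of it, and does not schedule its measurement during that stay. The other named trigger, an acute inflammatory or toxic response, is covered on Day 0 by examinations of pressure and structure. Acuity has no counterpart.

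At stake is the patient who has just been injected in a first-in-human study, for which Protocol 3.1.1 reports a steep dose-toxicity curve in rabbit eyes. The stated purpose of the vitrectomy is to take the drug out, so there is less to gain from it as the drug leaves the eye by itself. If vision falls without visible inflammation and the patient does not mention it, the first scheduled occasion to see the fall is Day 2.

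**Working it through.** **Step 1: the schedule.** Post-injection timing of each test of visual function in Table 1 of the protocol:

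| Test | Reference reading | First reading after injection |
|---|---|---|
| Best corrected acuity | Screening, Baseline | Day 2 |
| Amsler grid | Baseline | Day 2 |
| Visual field | Baseline | Day 7 |
| Electroretinography | Baseline | Day 14 |
| Visually evoked potential | Screening | Day 28 |

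None falls on Day 0. The Day 0 eye examinations have no clock time; footnote b says only that they follow administration. The blood sample alone is timed, at 4 h ± 1 h. The reference acuity is the Baseline reading, which may be up to 7 days old. SAP 4.1 also uses it as the ETDRS baseline.

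**Step 2: how much drug is left.** The documents give no figure for this, so there is none to reproduce. Inputs are the rabbit ocular half-life of 12 to 21 h (Protocol 1.3.2) and the upper bound of 20 h expected in patients (Protocol 3.2). Assuming first-order decline, the fraction remaining at time t with half-life h is 0.5^(t/h). For example, 0.5^(4/12) = 0.794, 0.5^(4/21) = 0.876, 0.5^(48/12) = 0.0625 and 0.5^(48/21) = 0.205.

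| Time after injection | h = 12 h | h = 20 h | h = 21 h |
|---|---|---|---|
| 4 h (minimum stay) | 79.4% | 87.1% | 87.6% |
| 24 h (about the Day 1 call) | 25.0% | 43.5% | 45.3% |
| 48 h (Day 2) | 6.2% | 18.9% | 20.5% |
| 72 h | 1.6% | 8.2% | 9.3% |

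By Day 2, 48/21 = 2.3 to 48/12 = 4 half-lives have passed, and 79 to 94% of the dose has gone. The SAP table prints a window on Day 2 that can be read as ±1 day. At its early edge, 24 h, 55 to 75% has gone.

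**Step 3: the two together.** By definition, more than half of the dose remains until one half-life has passed, that is, until 12 to 21 h. In that period the only scheduled route to an acuity loss is adverse event reporting on Day 0. The Day 1 call, taken as 24 h, comes when 25 to 45% is left, and it asks about acuity without measuring it.

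**The case against.** The case on the other side is substantial, and several stronger readings fail because of it.

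- A reader might infer that an immediate loss of vision leaves no trace in the primary endpoint. It does leave one: Protocol 2.1 includes adverse events in that endpoint, and Table 1 marks them after injection on Day 0 and on Day 1. A loss that is reported enters the data as an event; what is missing is a letter score.
- A reader might take "The results from each dosing day will be reviewed before progressing towards the subsequent dosing day" to mean that the next patient is dosed with no post-injection acuity in hand. Patients are at least 7 days apart, and Protocol 3.2 requires the board to review all data before the next injection. The Day 2 acuity falls inside that interval, so the next patient is protected.
- A reader might conclude that Day 2 is too late in every case. That is true only of a loss the patient does not report. The trigger is framed as a severe adverse event, and Protocol 7.1 defines severe by its effect on daily life or clinical status. A loss of that size may well come out through questioning during the stay or in the Day 1 call. The documents also set no time limit for vitrectomy.
- A reader might argue that a patient using both eyes would overlook a fall in the weaker study eye. This is possible but conjectural. Inclusion criteria 10 and 11 allow both eyes at 50 letters, and SAP 3.1 allows up to 70 in the study eye under the UK, Belgian and Dutch protocols.

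It is also fair to say that no passage promises a Day 0 acuity reading and that investigators may check acuity unscheduled. What remains is narrower: such a check is discretionary, need not be uniform across sites and has no place in the schedule, although acuity loss is the first event named for the rescue.

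**Conclusion.** The point holds in limited form. The protocol's rescue provision and its assessment schedule do not fit together: a named trigger has no scheduled measurement during the stay that it justifies, nor any before Day 2. The consequence is confined to a loss the patient does not report, and to the patient just injected.

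Its size is the contrast between 79 to 88% of the dose remaining at 4 h and 6 to 21% at 48 h. This assumes single-exponential decline and human ocular kinetics like those in rabbits. The protocol's own expectation of under 20 h points the same way, with at most 19% left at 48 h. The gap in the schedule itself needs no assumption; it is read directly from the table.

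Separately, 6.1 and the synopsis contradict each other on whether the listed events are exhaustive. The point above does not depend on which was meant.

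**What to change.** Reconcile 6.1 and the synopsis with Table 1 and SAP 3.2, and reconcile the limiting wording in 6.1 with the open wording in the synopsis. If acute acuity loss stays a named trigger, the schedule should contain a study-eye acuity assessment in the Day 0 post-injection column during the stay, entered in the eCRF and compared with the Baseline value. Its exact timing, any threshold and any resulting action are for the sponsor and the safety board.

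The cost per patient is small: one more use of a test already in the protocol, during a stay already required, and one eCRF field. There are two drawbacks. A reading soon after an intravitreal injection is noisier than one on a quiet eye. The same schedule change is also needed in each country protocol version; SAP 3.1 refers to Austrian, German, UK, Belgian and Dutch protocols.

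SAP 4.8 records a decision to close the study at Cohort 3. For patients already dosed the schedule cannot be changed, and the study report should then say that detection of acuity loss before Day 2 rested on adverse event reporting and the Day 1 call.

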6.2 Medical/Surgical History

A medical and surgical history will be taken at Screening. All medical history findings that have been present/active within 5 years before enrolment will be entered into the eCRF regardless of clinical relevance or presence at study start. Medical history findings that have not been present within the 5 years before enrolment will be recorded if deemed clinically relevant to the conduct of the study by the Investigator. The medical history should include drug allergy history and past and present smoking status.

